CONFIDENTIALITY (CONFIDENTIALITA')	12
CONFLICT OF INTEREST (CONFLITTO DI INTERESSI)	12
PUBLICATION POLICY AND DATA OWNERSHIP (Politica di pubblicazione e proprietà dei dati)	12
ADMINISTRATIVE ASPECTS.....	13
REFERENCES.....	14

BACKGROUND and STUDY RATIONALE

In the context of a progressively aging population, monitoring the status of Vascular Calcifications (VC) and Vertebral Fractures (VF) over time would be of primary importance, as VC (Lewis et al., 2018) and VF (Buckens et al., 2014) are recognized to be hallmarks of severe cardiovascular events (hospitalization and/or death) and hip fractures respectively, and VF represent an under-diagnosed cause of progressive disability and pain on its own (Delmas et al., 2005).

Moreover, there is an acknowledged relationships between vascular calcifications (VC) and vertebral fractures, confirmed by a recent meta-analysis (Chen and Yu, 2016).

However, data about the emergence/progression of VC and the emergence/worsening of VF over time are lacking. This is likely due to the absence of monitoring instruments for VC and VF that are both precise and easily accessible/applicable.

As to VC, they can be precisely assessed by coronary multi-slice Computer Tomography (CT), which can be interchangeably applied at the aorta or coronary artery (Takayama et al., 2016) but is unsuitable for routine follow-up controls as it implies high radiation doses and notable costs; cheaper scores based on RX projections that deliver a lower dose exist and are increasingly applied (among them, Kauppila score (Kauppila et al., 1997) is most frequently used) but the precision of their current implementations is questionable as they rely on subjective semi-quantitative grading, thus they do not perform an actual measurement. Notably, a thorough assessment of precision (i.e. observer variability, composed by intra observer variability also known as repeatability, and inter-observer variability also known as reproducibility) is lacking. The few works that addressed observer variability report only the intraclass correlation coefficient (ICC), which is not free from flaws (Popovic and Thomas, 2017) and do not permit to calculate important parameters such as the Minimum Detectable Difference (MDD). A more structured work to assess interobserver variability for vascular calcifications at the abdominal aorta has been performed on the DXA implementation (Shousboe et al., 2017), but also in that case only ICC is reported, showing values down to 0.6 (moderate agreement) for inter-observer agreement.

As to VF, Quantitative Vertebral Morphometry (QVM) is a plausible, although semi-quantitative RX-based mean to assess them according to Genant's classification (Genant et al., 2000), but it is seldom used; the same issues related to VC estimates apply, i.e. currently the scoring of VF too

often relies on visual-based semi-quantitative grading. There is in fact recent literature confirming the interest in increasing the precision of VF assessment through the development of more automated and quantitative grading systems (Kim et al., 2012; Oei et al., 2013).

In summary, there is a clear need, both for the monitoring of VC and VF, to:

- assess the precision of current methods, composed by intra-observer variability (i.e. repeatability) and inter-observer variability (i.e. reproducibility);
- develop more quantitative and automated, thus presumably more precise, monitoring methods.

OBJECTIVE OF THE STUDY

To evaluate the precision in terms of repeatability and reproducibility of an in-house developed software, called Calcify2D, that offers physicians a computer-assisted procedure to simultaneously score (and reduce scoring variability of) vascular calcifications (at the abdominal aorta and iliac arteries) and lumbar vertebral fractures (according to Quantitative Vertebral Morphometry principles) based on a latero-lateral thoracolumbar spine radiography. The software will be tested on clinical data from the VTP vs KYPHO study conducted recently at Istituto Ortopedico Rizzoli (IOR).

- Primary objective: to verify if the developed computer-assisted procedure reduces intra- and inter-observer variability in the computation of vascular calcifications at the abdominal aorta according to the Kauppila score
- Secondary objectives:
 - to verify if the developed computer-assisted procedure reduces intra- and inter-observer variability in the computation of lumbar vertebral fractures according to the principles of Quantitative Vertebral Morphometry
 - to produce preliminary data about the accuracy (i.e. accordance with measurements from accepted gold standard, taken as true) of the proposed computer-assisted scoring method for vascular calcifications, testing them against three-dimensional assessment from CT data (pending availability of matched CT data)
 - to produce preliminary data about the accuracy of the proposed computer-assisted scoring method for the existence of mild vertebral fractures, testing them against three-dimensional assessment of bone oedema from MRI data (pending availability of matched MRI data)

STUDY DESIGN

No-profit monocentric observational study to be conducted on the diagnostic images already collected at IOR within the VTP vs KYPHO study. From that study, diagnostic images of the thoracolumbar spine in different modalities (standard X-ray radiographies (Rx), CT, MRI) are available at several time points of follow-up and will be analysed in the present study.

Study workflow

- 1) Patient informed consent will be acquired
- 2) RX images showing VC will be used to assess whether the computer assisted VC scoring (primary objective) and Quantitative Vertebral Morphometry (QVM, limited to lumbar spine, secondary objective n.1) are less variable with respect to the traditional visual scoring of VC and QVM.
- 3) The database will be searched for the existence of CT and MRI taken simultaneously (within one week) to the RX images. In case of positive findings, the study will proceed to the following steps.
- 4) Computer assisted Rx-based VC scoring will be compared to three dimensional CT quantitative VC computation (acting as gold standard) to produce preliminary data on its accuracy.
- 5) Computer assisted Rx-based QVM will be compared to three dimensional MRI data (acting as gold standard) to produce preliminary data on its accuracy in detecting mild vertebral fractures.

POPULATION

The present study relies on the data of the VTP vs KYPHO study. Data from the population of the VTP vs KYPHO study are particularly relevant and suitable for the scope of the present study since all subjects show vertebral fractures (sometimes multiple fractures), and there is a known association between vertebral fractures and VC. The VTP vs KYPHO study ran at IOR from 2009 to 2014 (Prot. gen. n. 30364 approved on 20.11.2009). Diagnostic images of the thoracolumbar spine in different modalities (RX, CT, MRI) were collected at several time points of follow-up for 109 patients.

All patients eligible for the study according to the following criteria will be contacted to acquire their informed consent to the participation in the study.

ELIGIBILITY CRITERIA

Inclusion criteria

- Patients included in the previous VTP vs KYPHO study.
- Presence of diagnostic images (Dorso-lumbar radiographies taken in latero-lateral projection).

- Rx images will be screened for the presence of VC, retaining only those showing VC.
- Informed consent obtained prior to any study analysis-evaluation and/or data collection.

Exclusion criteria

- Images of the patients included in the study VTP vs KYPHO showing severe artefacts (usually due to presence of metallic devices) that alter the grayscale range and hinder correct identification of VC and vertebral fractures will be excluded.

MATERIAL AND METHODS

Computation of VC score and QVM

Latero-lateral Rx images will be imported into the software Calcify2D. The software guides the clinician to subsequently:

- 1) identify the edges of vertebral endplates from T12 to L5 (lines connecting endplates define the regions of interest for the computation of abdominal aortic calcification score according to the current practice (Kauppila et al., 1997);
- 2) measure the calcified plaques visible in the image, separating the anterior and posterior wall of the abdominal aorta, by tracing lines over them; a review of each traced line is possible; VC are then automatically scored according to the reference scoring system and to the absolute measure of calcification length;
- 3) refine vertebral contouring by picking a mid-side node on each vertebral endplate; QVM is then automatically computed;
- 4) review and save the report (with images) of VC and QVM issued automatically by the software application.

Observer variability tests on VC score and QVM

The test of observer variability will be performed by four clinicians from four relevant specialties, chosen among those who may often see VC and VF and are already familiar with the traditional scoring systems for both VC and VF (one radiologist and one spine orthopaedics from Istituto Ortopedico Rizzoli, one nefrologist and one internist from University of Padua).

Each clinician will assess all RX images to score VC and QVM, both via computer assisted procedures and via traditional visual inspection. To avoid bias, an interval of at least one week will be left between the computer assisted and visual scoring. To define intra-observer variability (i.e. repeatability), the whole dataset will be re-assessed three times, with an interval of at least one month between each re-assessment to avoid bias.

Preliminary assessment of the accuracy of computer assisted VC score and QVM against 3D data

In case time-matched CT data are available, the RX-based computer assisted VC score will be related to the current gold standard scoring system from CT (Takayama et al., 2016).

In case time-matched MRI data are available, they will be used to preliminary assess whether the RX-based computer assisted QVM can accurately detect mild vertebral fractures, which are detected with high sensitivity and specificity from MRI images because of the appearance of bone oedema.

STUDY END POINT**Primary Endpoint**

Observer variability (repeatability and reproducibility) in the assessment of vascular calcifications at the abdominal aorta according to a widely adopted scoring system (Kauppila et al., 1997): comparison between computer assisted and visual scoring.

Secondary Endpoints

- a) Observer variability (repeatability and reproducibility) in the assessment of vertebral fractures in the lumbar spine according to Quantitative Vertebral Morphometry (Genant et al., 2000): comparison between computer assisted and visual scoring.
- b) Accuracy of computer assisted VC score (comparison with gold standard CT-based score)
- c) Accuracy of computer assisted QVM in detecting mild vertebral fractures (comparison with gold standard MRI detection)

STUDY PROCEDURES**Screening procedure and Enrollment procedures**

Patients considered eligible will be enrolled in the study, after providing a written informed consent.

Other study procedures

Study subjects will not be subjected to any clinical procedures, as the present study intends to perform a re-analysis of the imaging data already collected in a previous study, named VTP vs KYPHO.

DATA COLLECTION

Clinical data will be retrieved by patient's source document.

A protocol-specific CRF reporting the results of the VC scores and QVM will be provided.

DATA MANAGEMENT

Patient images will be pseudonymised. To avoid bias in the scoring, the four clinicians performing the study will be blind to any personal and clinical information.

CRFs will be handled centrally and filled with the data recorded for each patient (for each trial scoring for each clinician). Computer assisted scores will be automatically saved after each assessment. Visual scores will be annotated by each clinician in a session file.

DATA HANDLING PROCEDURES

Secure data transfer will be applied to send imaging data to the all the outcome assessors.

The PI will be responsible for the data pseudonymisation.

STATISTICS

Sample size considerations were made on the primary endpoint, i.e. observer variability of the VC score.

The most appropriate measure to assess observer variability has been identified in the Standard Error of the Measurement (SEM), less ambiguous than the often used Intra-class Correlation Coefficient according to a recent review (Popovic and Thomas, 2017).

It must be noted that there is currently no estimate of the Minimum Detectable Difference (MDD) of current methods for monitoring VC. Indeed, an estimate of the MDD for the current visual and the computer assisted scoring methods will be obtained from the SEM computed in the present study.

There is also neither agreement in the literature about threshold VC values (according to Kauppila score) for adverse event prediction (they range from 4 (Vannini et al., 2016) or 5 (Szulc et al., 2014), to 8 (Kwon et al., 2014), to even 12 (Elmasri et al., 2016) in a 0-24 scale), nor consensus on a Minimal Clinically Important Difference (MCID) i.e. the minimum increase in VC score that is associated to a significantly increased risk of adverse events and/or warrants a change in treatment. It is worth noting that also in this case the present study is likely to bring an advancement to the field, by defining a reliable MDD, under which any MCID could not be set.

In absence of consistent MDD and MCID values, sample size computation may happen only by deciding how accurate the SEM estimate should be. We here take a reverse line of reasoning, i.e. we verify whether the analysis of the full data sample (we have the commitment of four clinicians

from four different relevant specialties to analyse three times the data) results in an acceptable accuracy of the SEM estimate. For these calculations, we refer to the technical note Bland dedicated to the sample size for a repeatability study (Bland MJ, 2010).

Considering that 109 patients were enrolled in the VTP vs KYPHO study, that their mean age was 73 (SD 8, range 54-97), and that all of them had vertebral fractures, we can estimate in 55% the prevalence of aortic calcifications, based on the results of a larger vascular calcification study that involved a similar population (mediterranean men and women over 50) (Naves et al., 2008). Therefore we expect data from 60 subjects will be available for the study after initial data screening. Being this a retrospective study not involving additional exams/clinical procedures/treatments we expect a relatively high success rate of the enrolment. We here prudentially state it at 75%, resulting in a final estimate of sample size of 45.

The 95% Confidence Interval (95% CI) of the SEM estimate for 45 subjects analysed three times by four observers, according to (Bland JM, 2010), is 6%. We deem this a very good value since it is seldom observed in observer variability studies, and may be robust to the occurrence of unexpected events (e.g. failure to complete a round of assessment plus reduction of subjects by 10 would still lead to a 95% CI below 10%).

Other statistical analyses for the primary endpoint will include further evaluation of intra- and inter-observer variability by the two-way ANOVA used to compute SEM (Eliasziw et al., 1994), Bland-Altman plots to assess agreement between methods, and Kappa statistics to assess inter-rater and inter-method agreement according to published thresholds (taking note of the above defined caveat about lack of consensus in threshold definition).

Additional analyses (per objective)

Objective 2 (observer variability in QVM): same analyses than in primary endpoint apply.

Objectives 3 and 4 (preliminary evaluation of the accuracy of computer-based assessment of VC and mild VF respectively against CT and MRI data): as we expect only few data points will be available, we plan to perform a simple correlation and residual analysis.

ETHICS AND QUALITY ASSURANCE

The clinical trial protocol and its documents will be sent before initiating the study to the competent Authorities and Ethics Committees for its approval.

The responsible investigator will ensure that this study is conducted in agreement with either the most updated Declaration of Helsinki and all the international and local laws that apply to clinical trials and to patient protection.

The protocol has been written, and the study will be conducted according to the principles of the ICH Harmonized Tripartite Guideline for Good Clinical Practice
(ref: <http://www.emea.eu.int/pdfs/human/ich/013595en.pdf>).

INFORMED CONSENT

All patients will be informed, by the investigator, of the aims of the study, the possible risks and benefits that will derive from the study participation.

The Investigator must clearly inform that the patient is free to refuse participation in the study and that can withdraw consent at any time and for any reason.

They will be informed as to the strict confidentiality of their patient data, but that their medical records may be reviewed for trial purposes by authorized individuals other than their treating physician.

The informed consent procedure must conform to the ICH guidelines on Good Clinical Practice. This implies that "the written informed consent form should be signed and personally dated by the patient or by the patient's legally acceptable representative".

The Investigator must also sign the Informed Consent form, and will keep the original at the site and a copy of the original must be handed to the patient.

The competent ethics committee for each Institution participating to the study must validate local informed consent documents before the study can be opened. It will be emphasized that the participation is voluntary and that the patient is allowed to refuse further participation in the study whenever he/she wants. This will not prejudice the patient's subsequent care.

Since the Study VTP vs KYPHO included also oncological patient, due to the high incidence of mortality the disease, it would be possible that some potential eligible subjects will be deceased, according to the Italian "*Autorizzazione generale n. 9/2016 al trattamento dei dati personali effettuato per scopi di ricerca scientifica*" of the Privacy Tutor, the informed consent is not required to be obtained by the deceased subjects according the aforementioned disposition.

CONFIDENTIALITY (CONFIDENTIALITA')

In order to ensure confidentiality of clinical trial data as disposed the national and European applicable regulation, data will be only accessible for the trial Sponsor and its designees, for monitoring/auditing procedures, the Investigator and collaborators, the Ethics Committee of each corresponding site and the Health Authority.

Investigator and the Institution will allow access to data and source documentation for monitoring, auditing, Ethic Committee revision and inspections of Health Authority, but maintaining at all times subject personal data confidentiality as per applicable regulation.

The Investigator must guarantee that patient anonymity is kept at all times and their identity must be protected from unauthorized persons and institutions.

All patients included in the study will be identified with a numeric code, so that no identifiable personal data will be collected.

The Investigator must have and conserve a patients' inclusion registry where it figures the personal data of the patient: name, surname, address and corresponding identification code into the study, this register will be kept on the Investigator File.

CONFLICT OF INTEREST**Istituto Ortopedico Rizzoli (IOR)**

[name] (PI): none (see form)

[name] (Spine Orthopaedician), [name] (Spine Orthopaedician), [name] (Resident Spine Orthopaedician), [name] (Radiologist), (Bioengineer), [name] (Bioengineer), [name] (Computer Scientist): none relevant for the purpose of this study

University of Padua

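### Endpoint c checks a vertebral shape measurement against MRI bone oedema, so mild deformities without oedema would lower agreement even if the software were perfect

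*Combined protocol and SAP*

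**What the plan says.** **Target and reference.** Under Objective of the Study, the last secondary objective seeks preliminary accuracy data for the "existence of mild vertebral fractures, testing them against three-dimensional assessment of bone oedema from MRI data". Study End Point lists this as endpoint c: "Accuracy of computer assisted QVM in detecting mild vertebral fractures (comparison with gold standard MRI detection". Material and Methods, in the subsection on preliminary accuracy against 3D data, supports the choice by saying that such fractures are "detected with high sensitivity and specificity from MRI images because of the appearance of bone oedema". It gives no figures and no citation for this.

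**Meaning of accuracy.** The preceding objective, on vascular calcification, explains accuracy as "accordance with measurements from accepted gold standard, taken as true". The fracture objective reuses the term without a new definition.

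**The test being assessed.** QVM is geometric. After the endplate edges are marked, the user must "refine vertebral contouring by picking a mid-side node on each vertebral endplate; QVM is then automatically computed".

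**The images.** Study Design says that radiographs, CT and MRI "are available at several time points of follow-up and will be analysed in the present study". Study workflow accepts a CT or MRI taken within one week of the radiograph. Population says that every patient has vertebral fractures, in some cases more than one.

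**The analysis.** Statistics, under the additional analyses per objective, foresees few data points and plans only a correlation with inspection of residuals.

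**The concern.** QVM responds to the shape of a vertebra, and the reference responds to its marrow signal. The two coincide for a mild fracture recent enough to show oedema. They can part company for a mild deformity that is old: the shape change remains, while oedema generally does not. Oedema also carries no grade, so the reference cannot by itself separate a mild fracture from a recent, more severe one.

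Nothing in the plan closes this gap. The one-week rule pairs one image with another; it does not limit the age of the fracture. No section restricts endpoint c to recent fractures, records fracture age, sets out what counts as mild, or adds a shape criterion on MRI.

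What is at stake is the meaning of the result. A modest correlation could reflect the software, or it could reflect how many of the deformities had lost their oedema when the images were taken. A small data set would offer little means of telling the two apart afterwards.

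**Working it through.** **The plan's own figures.** The documents give no figure for endpoint c. The only precision figure, 6% for the standard error of measurement, belongs to the primary endpoint. It reproduces as 1.96/√(2n(m−1)) with n = 45 subjects and m = 3 × 4 = 12 readings: 1.96/√990 = 0.062. It plays no part in endpoint c.

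**Do the sections allow a different reading?**
- Study workflow speaks only of three-dimensional MRI data, which could include shape. Objective of the Study and Material and Methods both name oedema, so oedema is the criterion as written.
- The index test is computed from endplate contours, so its target is shape.
- The matching rule and the eligibility criteria say nothing about fracture age.

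**Effect on the planned correlation.** All inputs here are assumptions, because the documents give none:
- p = share of vertebrae with a mild fracture, taken as 0.10 to 0.30;
- r = share of those that show oedema, taken as 0.25 to 1;
- QVM is perfect: it flags every mild fracture and nothing else;
- no undeformed vertebra shows oedema;
- both results are treated as yes/no, so the correlation is phi. The plan does not say in what form the two will be correlated.

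Cell shares:
- QVM positive, oedema present: pr
- QVM positive, oedema absent: p(1−r)
- QVM negative, oedema present: 0
- QVM negative, oedema absent: 1−p

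Then phi = pr(1−p) / √[p × pr × (1−p) × (1−pr)] = √[ r(1−p) / (1−pr) ].

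Worked case, p = 0.10 and r = 0.50: √(0.50 × 0.90 / 0.95) = √0.4737 = 0.688.

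| r | p = 0.10 | p = 0.20 | p = 0.30 |
|---|---|---|---|
| 1.00 | 1.000 | 1.000 | 1.000 |
| 0.75 | 0.854 | 0.840 | 0.823 |
| 0.50 | 0.688 | 0.667 | 0.642 |
| 0.25 | 0.480 | 0.459 | 0.435 |

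Every value below 1 arises with a faultless QVM. The loss comes from the share without oedema, 1−r, and grows slightly with p.

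**The case against.** Several counter-arguments have force.

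- **No error counts are planned.** A reader might infer that old fractures would be tallied as false positives and would depress specificity or predictive value. The documents do not support that: only correlation and residuals are planned. The effect would appear as disagreement, and an inspected residual might even bring it to light. This stands, and the size above is therefore given as a correlation.
- **The distortion is not certain.** A reader might infer that a perfect QVM must look inaccurate, or that the objective cannot be answered. Neither follows. If all mild fractures in the matched pairs show oedema, and no undeformed vertebra does, there is no distortion. The documents do not say which follow-up visits have an MRI within a week of a radiograph. The matched pairs may lie close to the fracture, or there may be none.
- **The clinical premise is external.** The documents do not say that oedema fades or that it does not grade severity; they stress high sensitivity and specificity. The premise is general clinical knowledge and is labelled as an assumption here. The difference between a shape measurement and a marrow signal is visible in the text itself.
- **Oncology.** Informed Consent remarks "Since the Study VTP vs KYPHO included also oncological patient", and a reader might infer that tumour signal will contaminate the reference. The remark serves only to explain consent for deceased patients and gives no number. It is too thin to carry a finding.
- **Low stakes.** The endpoint is secondary, called preliminary and conditional on matched MRI. This limits the weight of the point but does not remove the mismatch.

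**Conclusion.** The point holds in a limited form. As written, endpoint c compares a measure of vertebral shape with a marker that generally reflects recent injury, and no rule confines the comparison to fractures expected to show that marker. Any mild deformity without oedema among the matched pairs would lower the agreement for reasons unrelated to the software.

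The size cannot be fixed from the documents. Over the assumed range it runs from no effect to a correlation of about 0.435 for a perfect QVM. This rests on the premise about oedema, on the assumed p and r, and on a yes/no comparison. The point is minor to moderate. The primary endpoint, the sample size and secondary endpoints a and b are untouched.

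**What to change.** Before any MRI is read, align the secondary objective, the accuracy subsection of Material and Methods, endpoint c and the per-objective analyses in Statistics, so that each comparison has one stated target condition:

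1. Where oedema is the reference, limit the conclusion to recent (oedema-positive) fractures.
2. Where the question is whether any mild fracture exists, record vertebral shape on the same MRI and use that as the reference. State what counts as mild.
3. Report deformities found by QVM without oedema as a separate category, not as inaccuracy of QVM.

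The two comparisons should be kept apart. Shape on MRI is not a reference for recency, and oedema is not a reference for the existence of every mild fracture.

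**Cost.** No new imaging is needed. There is one extra item when the MRI is read, and a place to record it: Data Collection describes a case report form for the calcification scores and QVM only, and no MRI reading procedure is set out. The statistical price is smaller cells in a data set already expected to be small, so results should be shown as counts and described, not tested.

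### The primary question is whether the software reduces observer variability, but the plan names no software-versus-visual SEM contrast, no interval for it and no rule for concluding a reduction

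*Combined protocol and SAP*

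**What the plan says.** The primary objective (Objective of the Study) is directional and covers two components: "to verify if the developed computer-assisted procedure reduces intra- and inter-observer variability in the computation of vascular calcifications at the abdominal aorta". The primary endpoint (Study End Point) is observer variability of the Kauppila score, with a "comparison between computer assisted and visual scoring".

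The design supports a paired comparison. Under the heading on observer variability tests: "Each clinician will assess all RX images to score VC and QVM, both via computer assisted procedures and via traditional visual inspection". The whole dataset is assessed three times. The readers are four: the test is "performed by four clinicians from four relevant specialties, chosen among those who may often see VC and VF", with one clinician per specialty. Images are "available at several time points of follow-up and will be analysed in the present study".

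The Statistics section chooses the SEM as its measure and states that an "estimate of the MDD for the current visual and the computer assisted scoring methods will be obtained from the SEM computed" in this study. It justifies the sample size by precision: "The 95% Confidence Interval (95% CI) of the SEM estimate for 45 subjects analysed three times by four observers" is put at 6%, and is said to stay below 10% if a round is not completed and 10 subjects are lost. It then adds: "Other statistical analyses for the primary endpoint will include further evaluation of intra- and inter-observer variability by the two-way ANOVA used to compute SEM", Bland-Altman plots for agreement between methods, and kappa for inter-rater and inter-method agreement. The same analyses are to apply to quantitative vertebral morphometry (QVM), the first secondary objective.

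**The concern.** The objective asks whether one method is less variable than the other. The Statistics section produces one SEM per method and stops there. It gives no difference or ratio of SEMs, no CI or test for one, and no statement of what result would count as a reduction.

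The other listed analyses do not fill the gap. Bland-Altman plots and inter-method kappa describe agreement between methods: two methods can agree on average while one is noisier, or disagree while being equally repeatable. Inter-rater kappa computed per method does bear on reproducibility, but no comparison of kappas is planned.

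Two things are at stake. A numerically lower SEM could be reported as a reduction when it is compatible with chance. And the only precision figure in the plan, 6%, does not describe the comparison that the study is meant to make. For the inter-observer part, the plan also does not say whether the conclusion concerns these four clinicians or clinicians in general.

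**Working it through.** **Inputs from the Statistics section.** 109 patients, 55% prevalence of calcification and 75% enrolment: 109 × 0.55 ≈ 60, and 60 × 0.75 = 45 subjects. Four observers and three rounds give 12 readings per subject and method. The fallback is 35 subjects with a lost round.

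**1. The plan's own figure.** The relative half-width of a 95% CI for a within-subject SD is 1.96/√(2n(m − 1)), with n subjects and m readings each.
- Full design: 1.96/√(2 × 45 × 11) = 6.2%. This matches the stated 6%.
- Fallback, 8 readings each: 1.96/√(2 × 35 × 7) = 8.9%. This matches the stated bound of 10%.

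Both figures describe a single SEM of one method with all readings pooled. They do not separate the two components of the objective. For the intra-observer SEM alone, the degrees of freedom are 45 × 4 × 2 = 360, giving 1.96/√720 = 7.3%. In the fallback with all readers losing a round they are 35 × 4 × 1 = 140, giving 1.96/√280 = 11.7%.

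**2. Intra-observer ratio SEM(software)/SEM(visual).** Assume one image per subject and normal independent errors with equal variance across patients. The squared ratio, divided by its true value, then follows an F distribution with equal degrees of freedom. The detectable ratio is for 80% power at two-sided 5%.

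| Design | df per method | 95% range under equality | Detectable ratio | Power at true ratio 0.85 |
|---|---|---|---|---|
| 45 × 4 × 3 | 360 | 0.90–1.11 | 0.863 | 0.87 |
| 35 subjects, one reader loses a round: 35 × (3 × 2 + 1) | 245 | 0.88–1.13 | 0.836 | 0.72 |
| 35 subjects, all readers lose a round | 140 | 0.85–1.18 | 0.789 | 0.48 |

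In the full design, power at a true ratio of 0.90 is 0.51. With equal methods the two SEM estimates are exchangeable, so the software's is the lower one in about half of studies.

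**3. What moves these figures.** The documents give no error variances, so the following rests on assumed values.
- *More images per subject.* Two images with independent errors give 720 df and a detectable ratio of 0.901, closer to 1.
- *Error variance that differs between patients.* Let c be its squared coefficient of variation, assumed to be 0.5, 1 or 2. If each patient's error variance is shared by both methods, SE(log ratio) ≈ √((1 + c)/360), and exp(−2.80 × SE) = 0.835, 0.812 and 0.774. A simulated patient bootstrap gave 0.837, 0.819 and 0.797, or about 0.80–0.84. If the variances are independent between methods, SE ≈ √((1 + c)/360 + c/(2 × 45)), which gives 0.76, 0.70 and 0.61.

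**4. Inter-observer ratio.** Define the inter-observer SEM as √(observer + subject-by-observer + residual variance). Only the observer main effect is limited to 3 df, so precision depends on its share of the variance, which the documents do not give. With equal methods, random readers and an assumed subject-by-observer share of 15%, the simulated 95% range of the ratio is about 0.90–1.12 at an observer share of 5%, and about 0.72–1.40 at 30%. A CI from resampling patients only would then falsely show a reduction in about 5, 10, 20 and 26% of studies at observer shares of 5, 10, 20 and 30% (nominal 2.5%). If the readers are treated as fixed, the rate is about 3–4%. This is the reason to limit the inter-observer claim to these four readers.

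**The case against.** The strongest reply is that the comparison is plainly intended. The endpoint names it, both methods get an SEM and an MDD, and the plan explains that sizing is by precision because no MDD or minimal clinically important difference is established. That stands as an account of the intent and of the sizing. It does not say how the two SEMs will be compared. A limit of 1 for the ratio needs no minimal important difference.

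Other objections stand in part. The plan is silent on how the SEMs will be compared, so it would be wrong to say that it commits to a comparison by eye. The 6% is already labelled as the CI of an SEM estimate, so misreading it is a risk and not an error in the plan. The patient bootstrap, the limit of 1 and the restriction to four readers are choices among several reasonable ones. The inter-observer error rates above rest wholly on assumed shares, and they describe a possible analysis that the plan does not propose. Finally, one fixed range for the detectable ratio under unequal variances would be falsely narrow, because it depends on whether the same patients are hard to read by both methods.

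**Conclusion.** The gap is real: followed exactly, the plan gives no inferential answer to its primary question. On the stated assumptions, the intra-observer ratio varies over about 0.90–1.11 by chance alone, and a ratio of about 0.86 is detectable with 80% power in the full design (about 0.79 with 35 subjects if all readers lose a round). These figures move away from 1 if error variance differs between patients, and towards 1 with more images per subject.

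A reader might infer more than this, and the documents do not support it. They do not show that the study cannot answer the question: every clinician reads every image by both methods, so the data for a paired contrast will exist. They do not show that the 6% is wrong: it reproduces for what it describes. They do not show that the study is too small, because no target reduction is given against which to judge it. The point is a cheap improvement to the analysis plan.

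**What to change.** In the Statistics section, where the analyses for the primary endpoint are listed:
- Make the primary contrasts SEM(software)/SEM(visual), one intra-observer and one inter-observer, from the ANOVA already planned. Define the inter-observer SEM as √(observer + subject-by-observer + residual variance), computed the same way for both methods.
- Give each ratio a 95% CI by resampling patients, keeping all readings and images of a patient by both methods together.
- Conclude a reduction for a component only if its upper limit is below 1. Report the two components separately, and call the joint primary objective met only if both succeed.
- State that the inter-observer conclusion applies to these four readers.
- Apply the same contrasts to QVM only where both methods are recorded on the same scale.

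In the sample size text:
- Say that 6% refers to a single pooled SEM.
- Add the detectable intra-observer ratio (80% power, two-sided 5%): about 0.86 for 45 × 4 × 3, and about 0.79 for 35 subjects with all readers losing a round. State the assumptions: one image per subject, and normal independent errors with equal variance across patients.
- Add that the ratio is further from 1 if error variance differs between patients. In the full design, for an assumed squared CV of 0.5–2, it is about 0.80–0.84 if the variances are shared by both methods and about 0.61–0.76 if independent. Add that it is closer to 1 with more images per subject.

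The cost is a few sentences and some analysis code, with no extra readings. The downsides are a stricter criterion for success, a slightly liberal bootstrap (about 3–5% false reductions against a nominal 2.5%), and an inter-observer claim limited to these four readers.
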